- Concurrent use of any non-insulin glucose-lowering agent, other than metformin (for example, GLP-1 agonists, Symlin, DPP-4 inhibitors, SGLT-2 inhibitors, sulfonylureas).
- 6. Hemophilia or any other bleeding disorder
- 7. Hemoglobinopathy
- 8. History of heart, liver, lung or kidney disease determined by investigator to interfere with the study
- 9. History of allergic reaction to Humalog or Novolog
- 10. Use of any medications determined by investigator to interfere with study
- 11. Significant chronic kidney disease (which could impact CGM accuracy in investigator's judgment) or hemodialysis
- 12. Concurrent use of any medication that could interfere with the study CGM, such as hydroxyurea
- 13. History of adrenal insufficiency
- 14. History of abnormal TSH consistent with hypothyroidism or hyperthyroidism that is not appropriately treated
- 15. History of gastroparesis
- A condition, which in the opinion of the investigator or designee, would put the participant or study at risk
- 17. Participation in another pharmaceutical or device trial at the time of enrollment or anticipated for during the time period of study participation
- 18. Employed by, or having immediate family members employed by Tandem Diabetes Care, Inc., or having a direct supervisor at place of employment who is also directly involved in conducting the clinical trial (as a study investigator, coordinator, etc.); or having a first-degree relative who is directly involved in conducting the clinical trial

Participant Duration

Approximately 6-12 weeks

Study Endpoints

The adult, pediatric and preschool populations will be combined for the analysis of primary and secondary endpoints. Separate analyses also will be performed for the adult, pediatric and preschool cohorts for the primary and secondary endpoints. CGM data collected during the challenge periods will not contribute to overall analysis of CGM metrics. The three study time periods are the Run-In period with Control-IQ technology 1.5, treatment period with Control-IQ technology 2.0 at the standard target, and treatment period with Control-IQ technology 2.0 at the lower target, where the order of treatment periods will be randomized.

Primary Endpoints:

- Severe hypoglycemia (with cognitive impairment such that assistance of another individual is needed for treatment) during study compared with data on severe hypoglycemic events reported by T1D Exchange clinic registry over a 3-month time period

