2.2 Participant Eligibility Criteria

2.2.1 Inclusion Criteria

- Individuals must meet all of the following inclusion criteria in order to be eligible to participate in the study.
- 151 1. Age 2 to ≤ 81 years

147

148

152

153

159

160

161

162163

164

165

166

167

168

169 170

171

172

173

174

175

176

177

178 179

180

181

183

186

- 2. Diagnosis of type 1 diabetes for at least 1 year, or at least 6 months for age 2-5 years at enrollment
- 3. Prior Dexcom CGM user, with at least 11 of the prior 14 days of CGM use available for download at the screening visit to confirm eligibility
- 156 4. Total Daily Insulin Dose (TDD) at least 2 units/day
- 157 5. Weight \geq 20 lbs
- 158 6. HbA1c < 10.5%
 - 7. For participants <18 years old, living with one or more parent/legal guardian knowledgeable about emergency procedures for severe hypoglycemia, present with the participant during and for 5 hours (3 hours for participants age 2-5) after the meal challenges, and willing to use the Dexcom Follow app (with push notifications turned on) for the duration of the study.
 - 8. For participants ≥18 years old, availability of a local contact who has access to the study participant, knows their whereabouts, can be available to assist during the late bolus meal challenges, agrees to be promptly available if contacted by study staff, and willing to use the Dexcom Follow app (with push notifications turned on) for the duration of the study. If the participant lives alone, the local contact must live within 30 minutes and have access to the subject overnight.
 - 9. Investigator has confidence that the participant and/or parent/guardian can successfully operate all study devices and is capable of adhering to the protocol.
 - 10. Willing to use only aspart (novolog) or lispro (humalog) insulin with the study devices, with no use of long-acting basal insulin injections, or inhaled insulin with the study devices.
 - 11. Have current glucagon product to treat severe hypoglycemia (injectable or nasal) at home (will provide prescription if they do not have one).
 - 12. Willing and able to perform the study late bolus meal challenges.

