2.2.2 Exclusion Criteria

- Individuals meeting any of the following exclusion criteria at baseline will be excluded from study participation.
 - 1. More than 1 episode of diabetic ketoacidosis (DKA) in the past 6 months
- 182 2. More than 1 episode of severe hypoglycemia (needing assistance) in the past 6 months
 - 3. Inpatient psychiatric treatment in the past 6 months
- 4. For Female: Currently pregnant or planning to become pregnant during the time period of study participation
 - A negative pregnancy test will be required for all females of child-bearing potential

- Counseling on appropriate birth control options will be provided to all females of childbearing potential
- 5. Concurrent use of any non-insulin glucose-lowering agent, other than metformin (for example, GLP-1 agonists, Symlin, DPP-4 inhibitors, SGLT-2 inhibitors, sulfonylureas).
- 6. Hemophilia or any other bleeding disorder
- 192 7. Hemoglobinopathy
- 8. History of heart, liver, lung or kidney disease determined by investigator to interfere with the study
- 9. History of allergic reaction to Humalog or Novolog
- 196 10. Use of any medications determined by investigator to interfere with study
- 197 11. Significant chronic kidney disease (which could impact CGM accuracy in investigator's judgment) or hemodialysis
- 12. Concurrent use of any medication that could interfere with the study CGM, such as hydroxyurea
- 200 13. History of adrenal insufficiency
- 201 14. History of abnormal TSH consistent with hypothyroidism or hyperthyroidism that is not appropriately treated
- 203 15. History of gastroparesis

205

208

209

210

211

212

216

- 16. A condition, which in the opinion of the investigator or designee, would put the participant or study at risk
- 206 17. Participation in another pharmaceutical or device trial at the time of enrollment or anticipated for during the time period of study participation
 - 18. Employed by, or having immediate family members employed by Tandem Diabetes Care, Inc., or having a direct supervisor at place of employment who is also directly involved in conducting the clinical trial (as a study investigator, coordinator, etc.); or having a first-degree relative who is directly involved in conducting the clinical trial

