Safety events (not including CGM defined events defined in sections 6.2.2, 6.2.3, and 6.2.4) will be based on Safety analysis set, and tabulated for each primary endpoint as the number of events per participant, the number of participants with ≥ 1 event, and the rate of events per 100 person-years. A 95% confidence interval will be calculated for the rate of events per 100 person-years.

Since study eligibility excluded participants with 2 or more severe hypoglycemia or DKA events in the

Since study eligibility excluded participants with 2 or more severe hypoglycemia or DKA events in the prior 6 months, an unbiased comparison of the event rate during the Treatment Period with the pre-study event rate is not possible. Therefore, the severe hypoglycemia and DKA event rates will be compared with the T1D Exchange data, which reported the frequency of 1 or more severe hypoglycemia and DKA events in the prior 3 months. The proportion of participants with events during the Treatment Period (each

958

959

960

961

period separately) will be compared with the run-in period as well as with the T1D Exchange frequency.
Differences in proportions across the three study periods (two active treatments and the run in) will be estimated in a pairwise fashion, and statistical significance will be assessed using a normal approximation to a binomial distribution.

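### Section 8.6.1 soundly drops the pre-study rate, but the registry comparison that replaces it is still confounded by the repeat-event exclusion, now on the trial side only and in the device's favour

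*Combined protocol and SAP*

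**What the plan says.** Section 2.2.2 excludes people with "More than 1 episode of severe hypoglycemia (needing assistance) in the past 6 months" and, in parallel, "More than 1 episode of diabetic ketoacidosis (DKA) in the past 6 months". One event of each kind is allowed.

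Section 8.6.1 reasons from that rule. It opens "Since study eligibility excluded participants with 2 or more severe hypoglycemia or DKA events in the" and goes on "prior 6 months, an unbiased comparison of the event rate during the Treatment Period with the pre-study event rate is not possible". It then concludes: "Therefore, the severe hypoglycemia and DKA event rates will be compared". The comparator it names is a registry proportion, the share of people reporting at least one event over a 3-month window. Each treatment period is to be compared separately with the run-in and with the registry frequency.

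The registry comparison is part of the endpoint wording. The synopsis names the registry in primary endpoints 1 and 2. Section 8.4 names it in endpoint 1 and refers to data on DKA events in endpoint 2. Section 8.2 says severe hypoglycemia and DKA will be compared with historical published data.

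For the pooled result the synopsis says: "The adult, pediatric and preschool populations will be combined for the analysis of primary and secondary endpoints". Its next sentence plans separate analyses for the three cohorts. No section gives a registry value, a cohort-specific registry value, or any restriction, matching or weighting of the registry figure.

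**The concern.** The argument in 8.6.1 runs: eligibility truncates prior events, so the pre-study comparison is biased, *therefore* use the registry. The last step does not follow. The exclusion still shapes the trial sample, while the registry proportion, as described, comes from people to whom it was not applied. If risk differs between people and persists over time, removing those with repeated events lowers the trial's expected proportion relative to an unselected population even when the device does nothing.

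Primary endpoints 1 and 2 are at stake. A trial proportion below the registry figure could be read as evidence of safety when part of the gap reflects who was allowed to enrol. The text also presents this comparison as the answer to selection bias, which invites that reading.

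**Working it through.** The plan has no figure to reproduce: it gives no registry frequency, margin or power, and 8.3 says the sample size is not statistically based. The check is therefore a sensitivity model.

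**Inputs from the documents.** Excluded if more than 1 event in 6 months (2.2.2); registry measure is at least 1 event in 3 months (8.6.1); 2 weeks per target and at least 72 completers (synopsis).

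**Assumed inputs.** Registry proportion p = 3%, 5%, 8%. Individual event rates follow a gamma distribution with shape k (smaller k means more heterogeneity) and rate b, with 3 months as the time unit. Each person's rate is constant over time, the device has no effect, and one event type is modelled at a time.

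**Formulas.**
- Solve p = 1 - (b/(b+1))^k for b.
- In the prior 6 months: P0 = (b/(b+2))^k and P1 = k·(2/(b+2))·P0.
- Eligible fraction: P0 + P1.
- P(no event in the next 3 months, given eligible) = [P0·((b+2)/(b+3))^k + P1·((b+2)/(b+3))^(k+1)] / (P0 + P1).
- Benchmark inflation = p / (1 - that probability).

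**Worked case, p = 5%, k = 0.2.** b = 3.4205, P0 = 0.9120, P1 = 0.0673, eligible 0.9793. P(no event) = (0.9120 × 0.9667 + 0.0673 × 0.8161)/0.9793 = 0.9564. The eligible proportion is 0.0436, and the inflation is 0.05/0.0436 = 1.15.

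**Inflation of an equal-length, unselected benchmark:**

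| Shape k | p = 3% | p = 5% | p = 8% |
|---|---|---|---|
| homogeneous | 1.00 | 1.00 | 1.00 |
| 1 | 1.01 | 1.02 | 1.04 |
| 0.5 | 1.02 | 1.04 | 1.09 |
| 0.2 | 1.07 | 1.15 | 1.29 |
| 0.1 | 1.18 | 1.37 | 1.68 |

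The factor is never below 1, so this mechanism can only favour the device under the model. It is small unless heterogeneity is marked, because the rule removes people with 2 or more events while the registry counts people with 1 or more.

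**Direction against the pre-study rate.** For eligible people the later rate is [P0·k + P1·(k+1)]/[(b+2)(P0+P1)], and the truncated pre-study rate is P1/[2(P0+P1)]. In the worked case these are 0.0496 and 0.0344, a ratio of 1.44. Over p from 1% to 8% and k from 0.05 to homogeneous, the ratio runs from 1.02 to 1.94. That comparison works against the device, so 8.6.1 is right to reject it.

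**Window mismatch, for scale.** With p = 5% and constant hazard, P(at least 1 event in 14 days) = 1 - 0.95^(14/91.3) = 0.0078. That is 72 × 0.0078 = 0.56 participants, against 72 × 0.05 = 3.6 implied by the 3-month figure, a factor of 3.6/0.56 = 6.4. Selection at 1.15 would move the 0.56 by 0.56 × (1 - 1/1.15) = 0.07 participants.

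**The case against.** **No formal inference.** Section 8.2 states that there are no formal hypotheses and that p-values will not support formal inference. This lowers the consequence, but a descriptive comparison named in a primary endpoint can still mislead.

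**Much of the remedy exists.** Section 8.6.1 already tabulates event rates per 100 person-years with a 95% CI, cohort analyses are planned, and significance testing is tied to the three study periods, so no registry p-value is explicitly planned. All of that stands. What is missing is the order of priority, a cohort-matched registry figure and the stated limitation.

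**There is an internal comparator.** The run-in comparison uses the same participants, so this selection does not distort it. It has its own limits: the run-in always comes first, and the safety set contains only people who started the Treatment Period.

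**The effect may be negligible.** With homogeneous risk it is nil, and at shape 0.5 it is under 10%. This stands.

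**Stronger readings.** A reader might infer that the registry is exposed to the same selection, or that the same bias simply carries over. Neither is right: the exclusion acts on the trial side only, and the direction reverses between the two comparators. A reader might also infer that endpoints 1 and 2 are on balance biased toward the device. The documents do not establish that. Sections 1.3.1.3 and 1.3.1.4 say the late-bolus challenges could raise the risk of hypoglycemia and hyperglycemia, adverse events are asked about at every contact, and at least half of each age group is meant to have HbA1c of 7.5% or more. Other entry criteria, such as "Prior Dexcom CGM user, with at least 11 of the prior 14 days of CGM use available for download at" screening and an HbA1c limit of about 10.5%, may also separate the trial from the registry. The registry's composition is not in the documents, so those differences cannot be sized or given a direction.

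**Conclusion.** The point holds in a limited form. The plan's reason for rejecting the pre-study rate is sound, but it does not justify the registry as a remedy. The comparison in primary endpoints 1 and 2 remains confounded by a one-sided eligibility rule, and that rule taken alone favours the device.

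On assumed inputs, the benchmark is too high by 1.00 to 1.68 for registry proportions of 3-8% and shapes from homogeneous to 0.1. The documents support no particular value in that range, since they give neither the registry rate nor the heterogeneity. No claim is made about net direction. The trial's own counts and rates, and the run-in comparison, are not affected by this mechanism. The window mismatch is a separate defect, larger than the selection effect in the scenarios worked here; correcting it would leave this one in place.

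**What to change.** In 8.4 and 8.6.1:

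1. Make the already planned event rate per 100 person-years, with its 95% CI, the primary result for endpoints 1 and 2.
2. Show the registry figure as descriptive context only: by age cohort, and weighted to the trial's age mix for the pooled line. Restrict it to comparable registry members only if such data can be obtained.
3. State that no p-value against the registry will be given.
4. Replace the *therefore* reasoning with a statement that the one-sided exclusion is expected to lower the trial's proportion relative to an unselected registry even if the device has no effect.
5. Separately, align the 2-week and 3-month windows before any registry figure is shown.

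The cost is SAP wording and, at most, a request for a registry tabulation; conduct and sample size do not change. The sponsor gives up a favourable-looking comparison. The trial's own interval will also be wide: 72 participants for 14 days give 72 × 14/365.25 = 2.76 person-years per period, or 5.52 over both.

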- Diabetic ketoacidosis during study compared with data on DKA events reported by T1D Exchange clinic registry over a 3-month time period
- 3. Number of unanticipated adverse device effects
- 4. Number of other serious device-related adverse events

Secondary Endpoints:

- 1. All device-related adverse events
- 2. CGM hypoglycemia outcomes, compared between the three study time periods
 - a. Overall % time <54 mg/dL
 - b. Overall % time <70 mg/dL
- Times in ranges-overall (70-180 mg/dL, >180 mg/dL, >250 mg/dL, 70-140 mg/dL) compared between the three study time periods
- 4. Mean glucose compared between the three study time periods
- 5. Overall variability (CV and SD) compared between the three study time periods
- 6. Secondary endpoints 2 5 compared during daytime and nighttime, across the three study time periods
- 7. Secondary endpoints 2 5 as well as adverse events, during the study meal challenge periods, for late bolus feature use compared to normal bolus in the meal challenges.
- Time to intervention for hypo- or hyperglycemia during the study meal challenge periods, for late bolus feature use compared to normal bolus in the meal challenges.
- Number of interventions for hypo- or hyperglycemia during the study meal challenge periods for late bolus feature use compared to normal bolus in the meal challenges.
- 10. Subgroup Analysis for all metrics by age cohort, baseline HbA1c cohort, and target activity use (standard target, lower target, sleep activity, exercise activity)

Protocol Overview/Synopsis

After consent is signed, eligibility will be assessed.

Run-In Period:

Participants will return to clinic to undergo device training with the study CGM and a Control-IQ technology 1.5 pump. Training for both devices may be combined, or depending on comfort level of investigator and participant, participants may return for a second session to complete device training and begin the Control-IQ 1.5 run in period. The run-in period will end after 2 weeks of Control-IQ technology 1.5 use.

Participants will have a phone follow up phone call at 1 day, 3 days and 1 week after starting Control-IQ technology 1.5 use, and will return to clinic at two weeks to commence Control-IQ technology 2.0 training.

Treatment Periods:

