6.6 Stopping Criteria

6.6.1 Participant Discontinuation of Study Device

- In the case of an unanticipated system malfunction resulting in a severe hypoglycemia or DKA event (or a malfunction that could have led to severe hypoglycemia or DKA), use of the study device will be suspended for that participant while the problem is diagnosed. The UADE will be reported to the IRB and FDA. After assessment of the problem and any correction, use of the study device will not be restarted
- until approval is received from the IRB and FDA.
- In the absence of a device malfunction, use of the study device by a participant will be discontinued if any of the following occur:
- The investigator believes it is unsafe for the participant to continue on the intervention. This could be due to the development of a new medical condition or worsening of an existing condition; or participant behavior contrary to the indications for use of the device that imposes on the participant's safety
- The participant requests that the treatment be stopped
- Participant pregnancy
- One distinct episodes of DKA in the study treatment period as defined in section 6.2.4
- One distinct severe hypoglycemia events in the study treatment period as defined in section 6.2.3
- Each DKA or severe hypoglycemia event will be reviewed by the Medical Monitor with respect to
- determination of cause and whether the occurrence of the event can be attributed to use of the study
- device or study drug.

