8.2 Statistical Hypotheses

The primary objective of the study is assessment of safety. Therefore, there are no formal statistical hypotheses associated with any of the endpoints. Safety endpoints for SH and DKA will be compared to historical published data. Efficacy endpoints will be compared across study periods with the run-in period designated as the comparator study period. P-values for differences between study periods on both safety and efficacy endpoints will be calculated, however, will not be used for formal statistical inference due to the exploratory nature of the study objectives and the lack of correction for multiple testing.

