8.3 Sample Size

comparing continuous outcomes.

The sample size of at least 30 adults and adolescents age 14+ years old, 30 children age 6-13 years old, and 12 preschool participants age 2-5 years of age who will complete the trial was selected to have a reasonable time period of use in each age cohort to establish safety, with each subject completing 2 weeks of Control-IQ 1.5 technology use, 2 weeks of Control-IQ 2.0 technology use with the target of 112.5 to 160 mg/dL, and 2 weeks of Control-IQ 2.0 technology use with the target of 90-130 mg/dL. The choice of sample size is not based on statistical principles. In addition, the sample size assures a reasonable number of late bolus meal challenges completed.

There is a further enrollment goal of at least half of all participants in each age group have an HbA1c at baseline of $\geq 7.5\%$, and have at least 6 participants age 14-17.

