8.6.3 Analysis of CGM Endpoints

CGM metrics will be assessed in CGM analysis set, and computed for the Run-In and both Treatment Periods separately. CGM metrics will be computed per subject over 24 hours, during daytime (6am-11:59pm), and during nighttime (12am-5:59am), as well as by age cohort (adults/adolescents, children 6 – 13, and preschool), baseline HbA1c cohort (HbA1c at baseline of ≥ 7.5%,yes/no), and target activity use as specified by the device (standard target, lower target, sleep activity, and exercise activity). The main statistical comparison will be made between the three 2-week periods (Run In, Treatment

The main statistical comparison will be made between the three 2-week periods (Run In, Treatment Period at standard target, Treatment Period at lower target). The comparison will be pairwise – Run-in vs standard targe, Ru-in vs lower target, and standard vs lower target. The percent time in glycemic ranges will be calculated as the number of measurements in the specified range divided by the total number of measurements for which it can be determined whether or not the measurement was in specified range.

The "Low" and "High" CGM readings will be included in all analyses. Percent time will be compared using a paired t-test assuming sufficient normality assumptions hold, otherwise an appropriate non-parametric method will be utilized.

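### The severe hypoglycemia and DKA proportions from 2-week periods are compared with a 3-month registry proportion with no common time scale, which favours the device about 2- to 6.5-fold at equal constant hazard

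*Combined protocol and SAP*

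**What the plan says.** Section 8.6.1 rules out a comparison with participants' own pre-study event rates, because eligibility excludes people with two or more recent events. It turns instead to the T1D Exchange data, "which reported the frequency of 1 or more severe hypoglycemia and DKA events in the prior 3 months". The operative sentence takes the proportion of participants with events, each treatment "period separately) will be compared with the run-in period as well as with the T1D Exchange frequency".

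Section 8.3 fixes the period lengths, for example "2 weeks of Control-IQ 2.0 technology use with the target of 90-130 mg/dL", and section 8.6.3 confirms them: "The main statistical comparison will be made between the three 2-week periods".

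The primary endpoints use a different window. Endpoint 1 (synopsis and section 8.4) is severe hypoglycemia "during study compared with data on severe hypoglycemic events reported by T1D Exchange clinic registry over a 3-month time period". Endpoint 2 in the synopsis reads "Diabetic ketoacidosis during study compared with data on DKA events reported by T1D Exchange clinic registry over a 3-month time period"; section 8.4 lists it without naming the registry.

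Section 8.6.1 also tabulates trial events per 100 person-years with a 95% confidence interval, and says that event rates will be compared with the registry data. Section 8.2 says p-values "will not be used for formal statistical inference due to the exploratory nature of the study objectives".

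**The concern.** A cumulative proportion grows with the time observed. Someone followed for 2 weeks has had far less opportunity for an event than someone asked about the past 3 months. Setting the two side by side unadjusted builds in a difference that has nothing to do with the device, in a direction known beforehand.

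The window is also not settled. The endpoint wording could mean one treatment period (2 weeks), both (4 weeks), or run-in plus treatment (6 weeks), whereas 8.6.1 takes each period separately.

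At stake is the reported safety comparison. Safety is the primary objective, and the registry is the only external benchmark for SH and DKA. A figure that appears to lie below the registry could come from a device with a higher event hazard.

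**Working it through.** **Inputs from the documents.** Registry window 3 months, taken as 91 days (8.6.1). Each period 14 days (8.3), both treatment periods 28 days, and run-in plus treatment 42 days. At least 72 completers (synopsis). The plan gives no figure for this comparison that could be reproduced.

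**Assumptions.** The registry proportion p is not in the documents, so a range of 1% to 15% is used, with 5% for illustration. The hazard is constant.

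**Step 1: equal hazard.** A 3-month proportion p corresponds over d days to q(d) = 1 - (1-p)^(d/91). The apparent advantage at equal risk is p/q(d).

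| p | 14 days | 28 days | 42 days |
|---|---|---|---|
| 1% | 6.47 | 3.24 | 2.16 |
| 3% | 6.42 | 3.22 | 2.15 |
| 5% | 6.36 | 3.19 | 2.14 |
| 8% | 6.28 | 3.16 | 2.12 |
| 15% | 6.07 | 3.08 | 2.08 |

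The ratio hardly depends on p. At p = 5%, q is 0.786%, 1.566% and 2.340%. For 72 participants that is 0.57, 1.13 and 1.68 expected affected, against 72 × 0.05 = 3.6 at the unscaled registry value. The chance of no affected participant in one 2-week period is (1 - 0.00786)^72 = 0.57.

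**Step 2: clustering.** If events concentrate in a few people (assumed gamma frailty, shape 0.05 to 1, p = 5%), the ratios become 4.1-6.2, 2.3-3.1 and 1.7-2.1. They are smaller but point the same way.

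**Step 3: how often a riskier device would look better.** Let the device have 4 times the registry hazard. The chance that the observed proportion among 72 falls below p is a binomial probability with event probability 1 - (1-p)^(4d/91). At p = 5%, below the registry means 3 or fewer affected (3/72 = 4.2%).

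| Window | Benchmark 5%, unscaled | Benchmark rescaled to q(d) |
|---|---|---|
| 14 days | 81% (3 or fewer) | 10% (none) |
| 28 days | 35% (3 or fewer) | 6% (1 or none) |
| 42 days | 10% (3 or fewer) | 1% (1 or none) |

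For the 14-day window with the unscaled benchmark, other values of p give 64% at 1%, 85% at 3%, 85% at 8% and 92% at 15%. At 1%, rescaling does not change the 64%, because only a count of zero lies below either benchmark.

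**Step 4: one concrete result.** Three of 72 affected in one period is 4.17%, which reads as below an assumed 5%. The matched 2-week benchmark is 0.786%, so the observed figure is 4.17/0.786 = 5.3 times it. The exact two-sided p-value is 0.019 against 0.786% and 1.0 against 5%.

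**The case against.** The strongest reply is that 8.6.1 also speaks of comparing event rates and tabulates a rate per 100 person-years, so a time scale is present. In the 3-of-72 example the reader would also see 3 events in 72 × 14/365.25 = 2.76 person-years, about 109 per 100 person-years (exact 95% CI about 22 to 318). A 5% registry proportion corresponds to about 21 per 100 person-years at constant hazard. This narrows the criticism but does not remove it. Only the trial side is put on person-time, the registry side stays an unconverted 3-month proportion, and the sentence that specifies the comparison is on proportions.

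Second, the consequences are limited, and this stands. Section 8.2 disclaims formal inference, the run-in comparison uses equal windows, and suspension under 6.6.2 depends on counts. At p = 5% and 4 times the hazard over 4 weeks, 4.4 affected participants are expected, with about a 45% chance of at least five, the suspension threshold. But the run-in also uses an investigational pump version (4.1.1), so it is not an external benchmark, and withholding a p-value does not correct a biased descriptive contrast.

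Third, the likeliest single result at equal risk is no affected participant in a period, which lies below the benchmark with or without rescaling. That is true, and it also shows how little such a result says.

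Fourth, the synopsis gives participation as about 6 to 12 weeks. At 12 weeks the ratio is only about 1.08. That reading would include time off the study device and is not the window 8.6.1 names; it still favours the device slightly.

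**Conclusion.** The concern holds. Followed literally, 8.6.1 compares a 2-week proportion with a 3-month one, and at equal constant hazard the registry figure would be 6.1 to 6.5 times the expected trial figure. The factor is 3.1 to 3.2 if 4 weeks is meant and 2.1 to 2.2 if 6 weeks is meant. All of these favour the device. They rest on an assumed registry proportion of 1% to 15% and a constant hazard; strong clustering of events would bring the factors down to as little as 4.1, 2.3 and 1.7 at p = 5%. These are expected values, and the observed counts will be very small. The effect is on the reported safety comparison for primary endpoints 1 and 2, not on any formal test or stopping decision. It should be corrected before analysis because the bias is foreseeable and one-directional.

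**What to change.** In 8.4 and 8.6.1, name one window for the registry comparison. Then do one of the following:

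- convert the registry proportion p to that window as 1 - (1-p)^(days observed/91); or
- compare first-event rates per person-time on both sides, taking the registry rate as -ln(1-p) per 91 days.

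Use actual exposure and exact confidence limits, and state the constant-hazard assumption. The first-event rate suits this trial better, because 6.6.1 lists "One distinct severe hypoglycemia events in the study treatment period as defined in section 6.2.3" among the reasons for ending device use (with a parallel entry for DKA), which shortens that person's exposure. Total events per 100 person-years should not be set against the registry, which counts people with at least one event.

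State that the comparison is descriptive, that clustering would change the conversion, and that excluding people with more than one recent event may also favour the device. Reporting the pooled 4-week Control-IQ 2.0 exposure beside each target would help but is optional.

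The cost is SAP wording and a short calculation, with no new data. The benchmark becomes less favourable (an assumed 5% becomes 0.79% for one period), and the comparison becomes visibly imprecise and rests on a stated assumption.
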